3.11.6 Forest plot

Forest plots displaying the treatment group comparisons and associated 95% confidence intervals by subgroup, together with the relative position of the overall treatment comparison, will be produced. The SAS[®] procedure SGPLOT will be used with the following code:

```
proc sgplot data=...;
scatter x=oddsratioest y=effect / xerrorlower=lowercl
xerrorupper=uppercl
markerattrs=or
(symbol=DiamondFilled size=8);
refline 1 / axis=x;
xaxis label="OR and 95% CI " min=0;
yaxis label="Covariates";
run;
```

3.11.7 Mean change and 95% confidence interval plot

The mean change from Baseline over time in total LBM (kg), derived gait speed (m/sec), total SPPB score, [REDACTED] total fat body mass (kg) (leg), [REDACTED] laboratory/vital signs/ECG/echocardiography assessments and the associated 95% confidence interval of the mean change will be presented graphically, by treatment group and across active bimagrumab treatment groups combined, overall and by relevant subgroups. The SAS[®] procedure SGPLOT will be used with the following code:

```
proc sgplot data=...;
plot mean*visitnum=trtn;
run;
```

where trtn = treatment group.

3.11.8 Odds ratios

The odds ratio of the difference in the bimagrumab treatment groups (bimagrumab 700 mg, bimagrumab 210 mg and bimagrumab 70 mg) as well as across active bimagrumab treatment groups combined (AT:E for falls [REDACTED], AT:S for AESIs and cardiac/orthopedic events) and placebo proportions for fall rates, [REDACTED] (proportion of patients returning to pre-surgical ability), the occurrence of at least one AESI, the occurrence of at least one cardiac event and the occurrence at least one orthopedic event will be derived with 95% confidence intervals for each of the bimagrumab treatment groups versus placebo. A p-value comparing bimagrumab versus placebo will also be presented. This information will be derived by the following SAS statement.

```
proc freq data=...;  
  table trtn*event;  
  exact fisher OR;  
run;
```

where event is a flag indicating whether a patient experienced at least one event of interest,
trtn= treatment group.

The treatment difference will be presented as odds ratios together with two-sided 95% CIs.

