The risk to patients in this trial will be minimized by compliance with the eligibility criteria, close clinical monitoring and guidance for the investigators provided in the Investigator's Brochure. An adjudication committee will review cardiovascular events to confirm that these events have been evaluated appropriately and diagnosed correctly, while a Data Monitoring Committee (DMC) will monitor safety data from the study and the entire bimagrumab program for potential safety concerns.

As for any other investigational drug, there are unknown risks to bimagrumab, which may be serious and unforeseen.

Benefits

The benefits of bimagrumab treatment in the hip fracture population are still not known. However, it is expected that as seen in healthy volunteers and patients with sIBM, the hip fracture patients will have an increase in muscle mass that may translate to better recovery of lower extremity function and faster return to mobility. Over the course of the study, the number of falls might be reduced, which in turn reduces the risk of traumatic injuries and fractures, including secondary hip fractures.

4 Population

The study population will consist of male and female patients ≥ 60 years old, at time of randomization, who underwent surgical treatment for a low-energy fracture of the proximal femur. The study aims to screen approximately 400 patients. With an estimated screen failure rate of about 40%, approximately 245 patients, with successful surgery after hip fracture, will be randomized in more than 60 centers worldwide. Approximately 200 patients are expected to complete the 24-week treatment epoch and approximately 120 patients the full 48 -week study period.

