5.5.9 Discontinuation of investigational treatment or premature study discontinuation

Patients may voluntarily discontinue the investigational treatment for any reason at any time.

The investigator should discontinue investigational treatment for a given patient if, on balance, he/she believes that continuation would be detrimental to the patient's well-being.

Investigational treatment *must* be discontinued under the following circumstances:

- Use of prohibited treatment as per [Table 5-1](#).
- Any other protocol deviation that results in a significant risk to the patient's safety
- Breaking of the blind (inadvertently or for emergency reasons)
- Severe hypersensitivity reaction occurs
- Liver event definition met as per [Appendix 2](#)
- Deviations from the prescribed dose regimen for investigational treatment with 2 doses missed at any time
- Death
- Withdrawal of consent
- Sponsor decision to terminate (part of) the study

Investigational treatment *may* be discontinued under the following circumstances:

- Emergence of the adverse events that in the judgment of the investigator, taking into account the patient's overall status, prevent the patient from continuing participation in the study
- Any laboratory abnormalities that in the judgment of the investigator, taking into consideration the patient's overall status, prevents the patient from continuing participation in the study

At the time of protocol amendment #2 implementation, patients who have already received their Week 20 infusion of investigational treatment returned to the site at their next scheduled

visit and performed their End of Treatment visit. They continued as per the study visit schedule Table 6.1.

Patients who discontinue investigational treatment are NOT considered immediately withdrawn from the STUDY or to have withdrawn informed consent to participation (described in section 5.5.10). The patient must return approximately 28 days following the patient's last investigational treatment administration to complete the End of Treatment visit assessments (Table 6-1). If the patient was already off-treatment for a longer period, then the End of Treatment visit can be performed without delay. After completing the End of Treatment assessments, patients will enter a 4-week follow up and return for the End of Study visit. If the patient fails to return for these assessments for unknown reasons, every effort should be made to contact him/her as specified in Section 5.5.11.

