9.5.1.3 Falls

The frequency of having at least one fall up to Weeks 24 and 48 will be summarized by treatment group. The time to the first fall may also be assessed using a plot of the Kaplan-Meier product limit estimates and a log rank test provided there are a sufficient number of events. Negative binomial regression may also be used to analyze fall event rates. All details regarding the analyses of falls will be documented in the statistical analysis plan. The numbers of patients meeting the criteria for the responder endpoint derived from SPPB, Gait Speed and incidence of falls by Week 24 and 48 will be summarized by treatment group. A logistic regression may be used to determine the treatment effect.

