A secondary objective of the study is to evaluate the effects of bimagrumab vs. placebo on the incidence of falls when the primary analysis is conducted. The analysis conducted for falls will include all available information collected in patients including information from visits after Week 24. Patients randomized to the active doses of 700mg and 210mg will be combined and compared to placebo, with the assumption that the differences in the incidences of fall within the bimagrumab doses (700 mg and 210mg) are minimal than the differences with the placebo arm. The annualized placebo fall rate is considered as 30% and a clinically meaningful ratio in the fall rate of the active doses relative to placebo is considered as 0.7 ([Gillespie et. al. \(2012\)](#)).

[Table 9-4](#) shows the power of detecting a significant difference between the active doses of bimagrumab and placebo in falls at Week 24, assuming sample sizes of 140 and 70 patients, respectively, negative binomial rates ([Zhu and Lakkis 2014](#)) with over dispersion parameter $k=1$ and using a two-sided test at alpha level = 0.05. It is also assumed that the average follow-up per patients will be 9 months.

[figure not shown]

Table 9-4 Power calculation for falls (sample size: BYM combined (210mg and 700mg) arm=140 and Placebo= 70)

Active bimagrumab annual fall rate	Placebo annual fall rate	Rate Ratio	Power, %
0.21	0.30	0.7	16.3
0.15	0.30	0.50	42.9
0.10	0.30	0.33	72.7
0.28	0.40	0.7	19.5
0.20	0.40	0.50	52.0

If the background placebo rate for the incidence of fall is 30% and if the rate reduction for the combined bimagrumab arm is 30% then the study will have less than 20% power. However, if the rate reduction is 67% (assuming the background placebo rate as 30%) then the study will have approximately 73% power.

10 Ethical considerations

[figure not shown]

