Unless otherwise specified, data will be summarized relative to the number of patients who entered the respective epoch (number of patients “at risk”). At the time of the primary analysis number of patients “at risk” comprises:

- Treatment epoch: Patients assigned to the relevant analysis set (for example safety [SAF] or full analysis set [FAS]) regardless of study status, implying all patients entering the treatment epoch and who received at least one infusion of study drug.
- Post-treatment follow-up epoch:
 - Patients who completed treatment but are ongoing in the post-treatment follow-up epoch or who have discontinued during the post-treatment follow-up epoch.
 - Patients who prematurely discontinue treatment within the defined 24-week treatment epoch and who then continue study participation as part of the planned 4-week post-treatment follow-up.
 - Patients who completed the treatment epoch and the post-treatment follow-up epoch (study completed at the time of the primary analysis).

The same convention in view of patients entering the post-treatment follow-up epoch will apply at the time of the final update analysis.

It is expected that efficacy analyses based on the 24-week treatment epoch will be considered final at the time of the primary analysis. In view of ongoing cleaning activities on AE and CM data, safety analyses related to these data, will not be final. For the post-treatment presentations, where both the treatment epoch and post-treatment follow-up epoch are presented, analyses will also not be considered as final at the primary analysis and will only be complete at the time of the final update analysis.

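### The crude proportion of patients with a fall, and its Fisher odds ratio, ignore how long each patient was observed: the Week 48 proportion will be too low, though the formal falls test is unaffected

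*SAP*

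**What the plan says.** **Crude summaries.** Protocol 9.5.1.3 plans: "The frequency of having at least one fall up to Weeks 24 and 48 will be summarized by treatment group". SAP 3.11.8 puts fall rates among the comparisons with placebo, for each dose and for the pooled 210 mg and 700 mg groups. It gives an odds ratio, 95% CI and p-value from PROC FREQ with the exact Fisher option, "where event is a flag indicating whether a patient experienced at least one event of interest". The code has no time term, no minimum follow-up and no time horizon.

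**Observation.** Protocol 6.4.4 collects falls by interview at visits and by calls to the site, and Protocol 7.1 ends adverse event recording at the last study visit. A patient who stops treatment has the End of Treatment visit about 28 days after the last dose. Protocol 5.5.9 then says: "After completing the End of Treatment assessments, patients will enter a 4-week follow up and return for the End of Study visit". Observation therefore ends about 8 weeks after the last dose. For patients who leave after the treatment epoch, the Table 6-1 footnote places the final visit no earlier than 4 weeks after End of Treatment, that is, Week 28 or later.

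**Retention.** Protocol section 4 states: "Approximately 200 patients are expected to complete the 24-week treatment epoch and approximately 120 patients" the full 48 weeks, out of about 245 randomized.

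**Analyses that do use time.** SAP 2.10.2.3 makes the negative binomial comparison of falls the fifth inference in the testing sequence, and SAP 3.11.9 gives it an offset for days at risk. SAP 3.11.4 censors patients without a fall in the time-to-first-fall analysis.

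**The concern.** A patient last seen at Week 16 without a fall enters the Week 48 table as fall-free, exactly like a patient watched for all 48 weeks. On the plan's own retention, about half of the patients lack full observation. As an estimate of the probability of falling within 48 weeks, the crude proportion is then too low in every arm.

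Falls are a secondary efficacy objective, and SAP 3.2 flags every p-value below 0.05, so a Fisher p-value on falls would stand beside the negative binomial result. Power for that test at the stated meaningful ratio of 0.7 is only 16.3% or 19.5% (Protocol Table 9-4). If it is inconclusive, readers are likely to turn to the simple percentages.

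**Working it through.** **1. Inputs**
- Fall rate: "The annualized placebo fall rate is considered as 30" per cent (Protocol 9.7), used in Table 9-4 as 0.30 per year, with 0.40 as the alternative.
- Dispersion k = 1; 140 v 70 patients; alpha: "using a two-sided test at alpha level = 0.05. It is also assumed" that "average follow-up per patients will be 9 months".
- Retention: 200/245 = 81.6% at Week 24 and 120/245 = 49.0% at Week 48. So 45 leave before Week 24, 80 leave between Weeks 24 and 48, and 120 complete.
- **Assumptions, not in the documents:** the stopping times, a constant fall rate, and stopping unrelated to falls.

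**2. The plan's own figure.** With n0 = 70, allocation θ = 2 and t = 0.75 year:

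V = (1/t)(1/r0 + 1/(θ·r1)) + (1 + θ)k/θ

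Power = Φ(√n0·|ln(r1/r0)|/√V − 1.96)

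For 0.21 v 0.30, V = 7.619 + 1.5 = 9.119 and power is 16.6% (plan 16.3%). The other rows give 43.6, 73.5, 19.8 and 52.8% (plan 42.9, 72.7, 19.5, 52.0%). All are within one point, so the planning model is the one used below.

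**3. Probability of at least one fall by week w** (k = 1, rate r, year = 365.25/7 = 52.18 weeks):

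P(w) = 1 − 1/(1 + r·w/52.18)

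At r = 0.30, P(48) = 1 − 1/1.276 = 21.6% and P(24) = 12.1%. A 52-week year changes these by 0.1 point at most. For exits spread evenly from week a to week b, the mean is

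1 − [52.18/(r(b − a))]·ln[(1 + rb/52.18)/(1 + ra/52.18)].

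**4. Crude Week 48 proportion** = (45·early + 80·late + 120·P(48))/245, at r = 0.30:

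| Assumed end of observation (weeks) | Early | Late | Crude | Relative shortfall |
|---|---|---|---|---|
| Even, 0-24 and 24-48 | 6.3% | 17.1% | 17.3% | 19.9% |
| Even, 8-24 and 28-48 (visit rules) | 8.4% | 17.9% | 18.0% | 16.9% |
| All at 8 and 28 (earliest under visit rules) | 4.4% | 13.9% | 15.9% | 26.4% |
| All at 24 and 48 (latest) | 12.1% | 21.6% | 19.9% | 8.1% |

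At 0.40 per year, full observation gives 26.9%. The two even-exit rows give 21.7% (shortfall 19.3%) and 22.5% (16.3%).

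Mean follow-up in the first two rows is 9180/245 = 37.5 and 9520/245 = 38.9 weeks, or 8.6 and 8.9 months. That is close to the plan's 9 months, although the plan's figure refers to the primary analysis.

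**5. Week 24.** (45·early + 200·P(24))/245 gives 11.1% and 11.4% in the first two rows against 12.1%, a shortfall of 8.8% and 5.7%.

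**6. Odds ratio with equal true fall rates.** Equal retention gives 1.00. For unequal retention, assume 90%/60% on placebo and 78%/44% on active (Weeks 24/48); the 1:2 average is 82%/49%. With visit-rule timing at 0.30:
- placebo: 0.10 × 0.0837 + 0.30 × 0.1787 + 0.60 × 0.2163 = 0.1918
- active: 0.22 × 0.0837 + 0.34 × 0.1787 + 0.44 × 0.2163 = 0.1743
- odds ratio: (0.1743/0.8257)/(0.1918/0.8082) = 0.89

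Across both even-exit timings and both rates the range is 0.87-0.89. With a common proportion of 0.177, the standard error of the log odds ratio at 140 v 70 is √[1/(70 × 0.177 × 0.823) + 1/(140 × 0.177 × 0.823)] = 0.38. The shift in the worked case, ln 0.89 = −0.12, is about one third of that.

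**The case against.** **The analysis that carries the inference is sound.** The falls test in the sequence has a days-at-risk offset and the log-rank analysis is censored. The Fisher odds ratio is outside the testing sequence. This stands, and it confines the point to supportive summaries.

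**The denominator is inferred.** The phrase "full analysis set [FAS]) regardless of study status" in SAP 2.4.1 describes the treatment epoch only. Post-treatment data have a different at-risk set, and SAP 2.4.2 refers to patients with data in that epoch. No dedicated falls section is visible in the SAP, so a fall-specific rule cannot be excluded. This stands as a condition. The visible post-treatment rule would not be a cure, because it counts early stoppers with only 4 weeks of follow-up as at risk.

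**SAP 3.11.8 names no horizon.** Weeks 24 and 48 come from the protocol's frequency table, so a Week 48 odds ratio is not stated as such. This also stands.

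**A reader might infer that early stopping of active treatment will make the drug look protective.** The documents do not support that. They forecast no difference in retention between arms. Moreover, 80 of the 125 expected losses (64%) come after treatment has ended. Early stops alone, observed to weeks 8-24 with everyone else followed to Week 48, give (45 × 0.0837 + 200 × 0.2163)/245 = 19.2%, a shortfall of about 11%.

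**Conclusion.** The point holds for the crude fall proportions. Followed as written, and unless SAP text that is not visible sets another denominator, the plan yields a Week 48 proportion below the probability of a fall over 48 weeks. At 0.30 falls per year and k = 1 the relative shortfall is about 17-20% with evenly spread exits and about 8-26% across the stopping times that the visit rules allow. These figures rest on the assumed stopping times, a constant rate and stopping unrelated to falls. No single percentage should be read as a figure from the plan.

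The odds ratio is biased only if retention differs between arms. Under the illustrative imbalance it moves to 0.87-0.89, which is small against its sampling error. It would be wrong to conclude that the confirmatory falls result is biased or that a false claim of benefit is likely. This is a low-cost improvement to supportive summaries.

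**What to change.** - In SAP 3.11.8, remove falls from the Fisher odds-ratio list. Alternatively, keep that odds ratio, label it as crude and not adjusted for follow-up, and state its time horizon.
- Report the Kaplan-Meier cumulative incidence of a first fall at Day 168 and Day 336 by arm, with the difference from placebo and its 95% CI, using the censoring times in SAP 3.11.4.
- First reconcile the status code in SAP 3.11.4. The value 1 is described there both as the fall event and as censored, while the LIFETEST statement treats it as censored.
- Show person-time at risk by arm beside any crude count of fallers.

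The cost is a change of SAP wording and one replaced table, from dates already collected. The downside is that a Kaplan-Meier estimate is less familiar than a crude percentage and still assumes non-informative censoring.

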3.11.9 Negative Binomial Regression (NegBin)

The negative binomial regression model will be used for analysis of falls event rate per year. The SAS procedure GENMOD will be used with the following code:

```
proc genmod data =...;  
class trt trtdt region;  
model event = trt trtdt region /dist=negbin lognb link=log offset=lntotal type3  
wald;  
lsmeans trt / diff cl exp;  
run;
```

where

event = number of events

trt = treatment group

region = region (Japan/Non-Japan)

trtdt = treatment date (early/late)

lntotal = log(total days under risk/365.25)

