6.2.2 Medical history

All relevant medical history and current medical conditions occurring prior to the date of informed consent will be captured in the Medical History eCRF. Investigators will have the discretion to record abnormal test findings on the medical history CRF whenever in their judgment, the test abnormality occurred prior to the informed consent signature.

The aim is to capture the diagnoses rather than symptoms.

In addition several specific eCRF pages will capture more details on a number of conditions such as:

- Fall history, which takes into account the last 12 months prior to the fall that led to the current fracture

- Cardiovascular and metabolic disease history including conditions such as cardiomyopathy, diabetes, hypertension, etc.
- All relevant orthopedic conditions and/or earlier surgical interventions that may affect lower limb function (e.g. prior fractures, arthroplasty, arthrodesis)
- Perioperative information on the hip fracture surgery including the surgical method used

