2.6 Subgroups

Table 2.2 Subgroups

Subgroup	By-group Presentations	Covariates

 • Region (geographical): 
 ○ Japan (Patients from centers in Japan). ○ Non-Japan (Patients from centers not in Japan). 	
 • Patient disposition. • Patient demographics and other Baseline characteristics (with the exception of general medical history, cardiovascular history, tobacco usage, [REDACTED]). • Study drug administration. • Primary and secondary efficacy. • Falls during the study. [REDACTED] • Physical activity. • Other DXA assessments (leg LBM [kg], [leg], [REDACTED]). • Adverse events. • Vital signs. [REDACTED] • Laboratory assessments (hematology, clinical, immunochemistry and urinalysis labs) 	
Primary and secondary efficacy.

 • Treatment Date: 
 ○ Early (≤ 21 days) (Patients randomized 21 days or less from their hip fracture surgery date). ○ Late (> 21 days) (Patients randomized greater than 21 days from their hip fracture surgery date). 		
Primary and secondary efficacy.

Subgroup	By-group Presentations	Covariates
	
 • Primary and secondary efficacy. • Other DXA assessments (total fat body mass [kg], [whole body],   ). • Falls during the study.   . • Vital signs (BMI). 	

 • Fracture Fixation Type: 
 ○ Internal (screws only, intramedullary [nails] and extramedullary fixation [plate, combinations]). ○ Arthroplasty (hemiarthroplasty or total hip arthroplasty). 
As recorded in the Hip fracture – perioperative data eCRF.
	
 • Primary and secondary efficacy. • Falls during the study.  . 	Secondary efficacy.

 • History of Falls (12 months): 
 ○ Yes. ○ No (none). 
The number of falls in the past year (12 months) prior to Screening is recorded in the Fall history eCRF. If number of falls in the past year (12 months) > 0 then the history of falls (12 months) is considered as “Yes”, otherwise “No (none)”.
	
 • Primary and secondary efficacy. • Falls during the study.  . 	Secondary efficacy.

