2.10.2.3 Statistical model, hypothesis, and method of analysis (secondary)

The change from Baseline in derived gait speed (m/sec) and change from Baseline in total SPPB score at each windowed post-baseline visit will be analyzed using an MMRM in a similar manner to the primary efficacy variable (as specified in [Section 2.10.1.3](#) [Statistical model, hypothesis, and method of covariate analysis]). Treatment group, visit, region (Japan/Non-Japan), treatment date (early/late), fracture fixation type (internal [screws only, intramedullary {nails} and extramedullary fixation {plate, combinations}]/arthroplasty [hemiarthroplasty or total hip arthroplasty]), history of falls (yes/no [none]), use of mobility aids prior to hip fracture (yes/no [none]) and Baseline value will be included as covariates (see “Covariates” column of Table 2.2 [[Section 2.6](#) {Subgroups}]). In addition, the following six interaction terms will be fitted:

- Treatment group*visit.
- Region*visit.
- Treatment date*visit.
- Fracture fixation type*visit.
- History of falls*visit.
- Use of mobility aids prior to hip fracture*visit.
- Baseline value*visit.

An unstructured covariance matrix will be used for the Week 12 analyses, Week 24 analyses (primary analysis) and Week 48 analyses (final update analysis). The underlying assumptions of the mixed model (homogeneity of slopes and normality) will be assessed by the normality of the residuals within treatment groups. The homogeneity of the variance will be checked by Levene's test at the time of the primary analysis. If the variable is not normally distributed,

natural log transformation may be used (see [Section 3.11.1](#) [Mixed Model Repeated Measures {MMRM}]) for more details on how to assess normality). The antilog of the point estimate and associated 95% confidence interval of the treatment difference will be computed prior to presentation.

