The following testing strategy will be used to control for multiplicity of endpoints and doses to be tested: if both doses (bimagrumab 700 mg and bimagrumab 210 mg) are statistically significantly different from placebo at $\alpha=0.05$ two-sided for the primary endpoint, then a fixed sequence approach will be applied for both derived gait speed (m/sec) and total SPPB score at Week 24 using the same linear mixed model for repeated measures and $\alpha = 0.05$ two-sided at each stage. The first inference will compare the bimagrumab 700 mg group to placebo for derived gait speed (m/sec), followed by a second inference comparing the bimagrumab 210mg group to placebo for derived gait speed (m/sec). The third inference will compare the bimagrumab 700mg group to placebo for total SPPB score, followed by a fourth inference comparing the bimagrumab 210mg group to placebo for total SPPB score. Additionally, the fifth inference will compare the combined bimagrumab 700mg and 210mg group to placebo for the incidence of falls observed until the time of the primary analysis. The sequence of the endpoints was decided based on the anticipated probability of showing statistical significance of bimagrumab over placebo, the clinical importance is not considered for this sequence determination, as each endpoint is clinically important.

The analysis conducted at Week 24 for falls (negative binomial) will include all available incidence of falls also collected from patients with visits beyond Week 24. The analysis of the fall data will be performed based on the assumption that the differences in incidences of fall within the active bimagrumab doses (700 mg and 210mg) are minimal compared to the differences with placebo.

No control will be used in comparing the change from Baseline at any visit (Week 12, Week 24 and Week 48) in secondary efficacy variables between the bimagrumab 70 mg dose and placebo.

(Secondary Objectives 1, 2 and 3)

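### The SAP's falls-rate code does not produce the pooled 700+210 mg v placebo test it is meant to serve, and it leaves out fall history and mobility-aid use, which the gait-speed and SPPB models adjust for

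*SAP*

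**What the plan says.** **The test.** In SAP Section 2.10.2.3 the last step of the fixed sequence reads: "the fifth inference will compare the combined bimagrumab 700mg and 210mg group to placebo for the incidence of falls". The same section names the method: "The analysis conducted at Week 24 for falls (negative binomial) will include all available incidence of falls". SAP Section 2.13 (Table 2.6) powers it as 140 pooled active patients against 70 on placebo. Protocol Section 9.5.1.3 leaves the details of the falls analysis to the SAP.

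**The code.** SAP Section 3.11.9 gives "model event = trt trtdt region /dist=negbin", with a log link and a log-exposure offset, then "lsmeans trt / diff cl exp". It defines trt simply as treatment group. It has no recoding of dose and no ESTIMATE, CONTRAST or LSMESTIMATE statement.

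**The covariates elsewhere.** For gait speed and SPPB, Section 2.10.2.3 states that "history of falls (yes/no [none]), use of mobility aids prior to hip fracture (yes/no [none]) and Baseline value will be included as covariates". Both factors are also strata in the time-to-first-fall code (Section 3.11.4) and by-groups for falls during the study (Table 2.2). Table 2.2 lists them as covariates for secondary efficacy, but its footnote limits that term to gait speed and SPPB, so the falls model does not inherit them.

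**The definition of fall history.** Protocol Section 6.2.2 has: "Fall history, which takes into account the last 12 months prior to the fall that led to the current fracture". SAP Section 2.6 has: "The number of falls in the past year (12 months) prior to Screening is recorded in the Fall history eCRF".

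**The concern.** With trt at its four levels, the LSMEANS statement returns six pairwise ratios, and none of them is the fifth inference. A programmer must therefore decide whether to recode or to use a contrast, how to weight the two doses, and whether the 70 mg patients stay in the model and contribute to the dispersion and covariate estimates. Each choice can move the p-value of an alpha-controlled test, so none should be open at unblinding.

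The covariate set is also inconsistent. Two baseline factors thought worth adjusting for in walking speed and physical performance are missing from the model for falls, the outcome to which a history of falling relates most directly. SAP Section 2.14 gives no reason. What is at stake is some precision in a test that the SAP itself shows to be short of power at its own meaningful ratio of 0.7.

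**Working it through.** **Inputs from SAP Section 2.13:** n = 70 placebo and 140 pooled active; mean follow-up t = 0.75 year; k = 1; two-sided alpha 0.05; rates as in Table 2.6.

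**1. Reproduce Table 2.6.** Var(log RR) = (1/(t·r0) + k)/n0 + (1/(t·r1) + k)/n1, and power = Φ(|ln RR|/√Var − 1.96).

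For 0.10 v 0.30: (4.444 + 1)/70 + (13.333 + 1)/140 = 0.0778 + 0.1024 = 0.1802. Then 1.0986/0.4245 − 1.96 = 0.63, so power is 73.5% (SAP: 72.7%). All five rows agree within one point.

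**2. One dose against placebo, as the printed code would report it.** Setting n1 = 70 for the same row gives 0.0778 + 0.2048 = 0.2825 and power 54.3%.

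| Active / placebo rate | SAP | Pooled, 140 v 70 | One dose, 70 v 70 |
|---|---|---|---|
| 0.21 / 0.30 | 16.3% | 16.6% | 13.0% |
| 0.15 / 0.30 | 42.9% | 43.6% | 31.6% |
| 0.10 / 0.30 | 72.7% | 73.5% | 54.3% |
| 0.28 / 0.40 | 19.5% | 19.8% | 15.4% |
| 0.20 / 0.40 | 52.0% | 52.8% | 38.7% |

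**3. Add fall history.** The documents give neither its prevalence nor its effect. Assumptions: prevalence q = 30-40%, fall-rate ratio R = 1.5-3 for prior fallers, and k = 1 is the marginal dispersion. The residual dispersion kc solves (1 + kc)(1 + v) = 2, where 1 + v = (1 − q + qR²)/(1 − q + qR)². Information in each arm is summed over history strata as n·p·μ/(1 + kc·μ), where p is the stratum share and μ its expected count per patient.

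Example: q = 0.3, R = 3, rates 0.20 v 0.40.
- 1 + v = 3.4/2.56 = 1.328, so kc = 0.506.
- Placebo, stratum counts 0.1875 and 0.5625: information 70 × 0.2512 = 17.59.
- Pooled active, stratum counts 0.0938 and 0.2813: information 140 × 0.1365 = 19.11.
- Variance = 1/17.59 + 1/19.11 = 0.1092, against 0.1167 unadjusted: a 6.4% reduction. Power goes from 52.8% to 55.5%.

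Over the whole assumed range:

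| Active / placebo rate | Variance reduction | Power, unadjusted → adjusted |
|---|---|---|
| 0.21 / 0.30 | 0.8-5.7% | 16.6 → 16.7-17.3% |
| 0.15 / 0.30 | 0.7-5.0% | 43.6 → 43.9-45.5% |
| 0.10 / 0.30 | 0.5-4.0% | 73.5 → 73.7-75.3% |
| 0.28 / 0.40 | 1.0-7.3% | 19.8 → 20.0-21.0% |
| 0.20 / 0.40 | 0.9-6.4% | 52.8 → 53.1-55.5% |

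A four-arm simulation (245 patients, 600 runs in each of six scenarios at a placebo rate of 0.30) gave adjusted-minus-unadjusted differences in power of −0.3 to +0.7 points, for example 47.0% v 47.3%. In practice the gain may be nil at these rates.

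**4. Room for covariates.** Expected falls in the tested arms run from 70 × 0.75 × 0.30 + 140 × 0.75 × 0.10 = 26 to 70 × 0.75 × 0.40 + 140 × 0.75 × 0.28 = 50. One or two extra parameters are affordable, but there is little to spare.

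The effect of mobility-aid use was not quantified.

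**The case against.** The pooled test is stated in words in Section 2.10.2.3 and powered in Section 2.13. Section 2.5 defines Active Total: Efficacy as the active groups without 70 mg, and Section 3.11.8 names it for falls. The SAP's code is skeletal elsewhere too: Section 2.10.1.3 promises an Active Total comparison for LBM that the code in Section 3.11.1 does not request. Programming specifications sit in RAP Module 8, which is not available here. Some falls text around Section 2.10.2.5 is not shown, and the covariates in Section 3.11.10 are redacted. Treatment date and region are the randomization strata, and the LBM model likewise uses no other categorical baseline covariates. All of this stands. It reduces the point to a gap in specification, but it does not supply the missing coding.

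A reader might infer three stronger things that the documents do not support.
- **That the omission biases or invalidates the test.** It does not: randomization protects the comparison, and only precision is affected.
- **That adjustment would rescue the power.** At 1.0 falls per year and ratio 0.5, power would rise from 81% to 82-86%, but the SAP plans 0.30-0.40 per year. At its meaningful ratio of 0.7 and a placebo rate of 0.30, power stays near 17%.
- **That the SAP counts the index fall as history.** Its wording, 12 months before Screening, would literally include it. But the value comes from the Fall history eCRF page, which Protocol Section 6.2.2 defines as covering the period before that fall. Almost no patient would otherwise fall in the SAP's no-history category. This is loose wording.

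**Conclusion.** The point holds as a gap in specification and a missed, inexpensive covariate adjustment. The printed code does not deliver the fifth inference. Reading a single-dose row in its place would test a different comparison, with 54.3% instead of 73.5% power at ratio 0.33. That contrast shows why the coding must be fixed in advance; it is not a loss that the plan intends. Leaving out fall history costs about 0.5-7% in variance and 0-3 points of power at the planned rates, given the assumed prevalence (30-40%), history rate ratio (1.5-3) and marginal k = 1. The gain would be larger only if falls prove more frequent than planned. The pooled coding is the more important of the two changes.

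**What to change.** In SAP Section 3.11.9:
- For the fifth inference, recode 210 mg and 700 mg as one level (Active Total: Efficacy) against placebo. An ESTIMATE that averages the two doses on the log scale would compare the geometric mean of their rates with placebo, which is not the combined group described in Section 2.10.2.3.
- State whether the 70 mg arm stays in the model as its own level.
- Add histfall and mobaid to CLASS and MODEL. If the model does not converge because events are few, keep histfall and drop mobaid.

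In SAP Section 2.6, and in the history-of-falls text of Section 2.8.2.2, align the wording with Protocol Section 6.2.2 so that the index fall is plainly excluded.

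The cost is SAP text and code, since both covariates are collected. The downside is one or two extra parameters in a model with few expected events.
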